13.1.1 Post-Treatment Follow-Up (only if suppressed at the End of Study)

These visits should continue approximately every four (4) weeks (no less than every 28 days) until the subject's HPA axis response has returned to normal or other satisfactory resolution is documented. These visits should occur such that the CST is performed at the same time (\pm one hour) as the CST performed at Visit 1 (Screening, Part B) and if possible, ideally the CST should be initiated between 7 and 9AM. The specific procedures performed at these visits are detailed in [Section 10.6](#).

13.2 Pregnancy Tests

UPTs will be performed at the study site if the site meets local country requirements to perform the testing (e.g., United States sites registered and conforms to Clinical Laboratory Improvement Amendments (CLIA) regulations for such testing [site possesses at a minimum a current valid CLIA Certificate of Waiver]) or at an appropriately registered reference laboratory. A UPT will be performed on all female subjects ([Section 10.1](#)) at Visit 1 (prior to CST), Visit 2 (prior to treatment) and at the end of study or if the subject withdraws prematurely. The investigator will report the UPT results on the CRFs, in the subject's medical records and in any independent records maintained at the study site. The urine pregnancy test used must have a minimum sensitivity of 25mIU of β -hCG/mL of urine.

13.3 Pharmacokinetic Tests

Blood (approximately 5 mL) for PK analysis will be drawn three times: at Screening (pre-application, time=0) and at Day 8 and Day 15 (unless IGA=0 at Day 8), approximately 12 hours after the dose on the previous day. All eligible subjects will have blood drawn at Screening for baseline drug concentration in plasma. On Day 8, all subjects, regardless of lesion clearance, will have blood drawn for assessment of trough drug concentration in plasma. Prior to the visit, subjects will be reminded to record i) the 12-hour “clock” time that the test article was applied in the evening of the day before the visit (Day 7) and ii) withhold application of the morning dose of test article on the morning of the visit (Day 8) until after the trough PK blood draw has been taken. Following this trough PK blood draw, subjects will apply, under supervision from the study staff, the morning dose of test article to the designated area and the time of application will be recorded and the percent BSA treated with test article and percent BSA affected will be recorded. Subjects who have cleared their treated lesions by Day 8 will not apply the Day 8 morning dose (unless CST and EOS procedures need to be performed on Day 9). At the Day 15 visit, subjects who have continued to treat lesions will have a final PK blood sample collected approximately 12 hours after their Day 14 evening application and just prior to the initiation of the CST.

All blood samples will be processed, stored and transported per the methodology provided by the analytical laboratory.

14. END OF STUDY CRITERIA

At the end of each subject's participation in the study, the investigator will complete an End of Study form for all completed and discontinued subjects.

14.1 Completion of the Study

Subjects who complete the treatment as specified in the protocol and who complete the End of Study evaluations will be considered to have completed the study.

14.2 Subject Discontinuation

A subject may be withdrawn from the study prior to completion for any of the following reasons:

- Whenever the subject and/or parent/guardian decide it is in the subject's best interest to withdraw. NOTE: if the subject and/or parent/guardian decide it is in the subject's best interest to withdraw due to an AE then it should be classified as withdrawal due to an AE.
- Whenever the investigator decides it is in the subject's best interest to be withdrawn
- AEs
- Worsening of condition or treatment failure (in the opinion of the investigator)
- Intercurrent illness which may, in the investigator's opinion, significantly affect assessment of clinical status

- Noncompliance
- Pregnancy
- Lost to follow-up
- Sponsor administrative reasons

14.3 Screen Failures

If a subject is a screen failure due to Visit 1 laboratory results that show an abnormal pre-CST serum cortisol level or abnormal HPA axis function (a low post-CST serum cortisol level), complete the Screen Failure CRF. No clinical evaluation or follow-up CST will be performed in these subjects; however, the laboratory results will be provided to the subject's parent with a recommendation to follow up with the subject's regular healthcare provider.

If a subject withdraws prematurely during the treatment period for another reason, complete the CRF for the appropriate visit, then complete the End of Study CRFs including scheduling appropriately to obtain the End of Study CST assessment.

Subject enrollment will continue until at least 20 subjects with both Screening and End of Study serum cortisol data (pre- and post-cosyntropin stimulation) have completed the study without any significant protocol violations (evaluable subjects). This may require the enrollment of approximately 25 subjects.

14.4 Study Termination

The study may be terminated by the investigator or the Sponsor. If, in the opinion of the investigator, clinical observations made during the study suggest that it may be unwise to continue, he or she may stop the study. A study termination by the investigator will be reported to the Sponsor.

In addition, a written statement fully documenting the reasons for this action will be submitted to the Sponsor by the investigator within five working days.

In the event that the Sponsor chooses to discontinue or terminate the study, appropriate notification will be given to the investigator.

15. ADVERSE EVENT REPORTING

An **adverse event** (AE) is any untoward medical occurrence associated with the use of a drug in humans, whether or not considered drug related.

An AE (also referred to as an adverse experience) can be any unfavorable and unintended sign (e.g., an abnormal laboratory finding), symptom, or disease temporally associated with the use of a drug, without any judgment about causality. An AE can arise from any use of

the drug (e.g., off-label use, use in combination with any drug) and from any route of administration, formulation or dose, including an overdose.

Information on the medical condition of subjects should begin following the subject's written consent to participate in the study and a medical history should be taken at screening. During any wash out and baseline periods, any changes in the health of subjects should be recorded as changes in medical history unless an event occurred as a result of a study-related procedure and is unanticipated; where in such cases, the event should be recorded as an adverse event and reported to the Institutional Review Board (IRB) as an "unanticipated problem" in accordance with local procedures. Other changes in subject health information becomes AE data when the subject begins dosing with the test article and therefore AE data should be collected from the date of the first dose of test article. These data are considered treatment-emergent AEs.

Timely and complete reporting of all AEs assists Therapeutics, Inc. (TI) in identifying any untoward medical occurrence, thereby allowing:

- 1) protection of the safety of study subjects;
- 2) a greater understanding of the overall safety profile of the test article;
- 3) recognition of dose-related test article toxicity;
- 4) appropriate modification of study protocols;
- 5) improvements in study design or procedures; and
- 6) adherence to worldwide regulatory requirements.

Test article is defined as a pharmaceutical form of an active ingredient (or "primary operational component" for devices) or vehicle/placebo being tested or used as a reference in the study, whether blinded or unblinded. AEs may be either spontaneously reported or elicited during questioning and examination of a subject. All AEs must be completely recorded on the AE CRF. If known, the investigator should report the diagnosis of the underlying illness or disorder, rather than its individual symptoms. Subjects experiencing AEs that cause interruption or discontinuation of test article, or those experiencing AEs that are present at the end of their participation in the study should receive follow-up as appropriate. If possible, report the outcome of any AE that caused permanent discontinuation or that was present at the end of the study particularly if the AE is considered by the investigator to be treatment-related (i.e., definitely, probably, or possibly related to test article).

15.1 Adverse Event

All AEs must be recorded on the AE CRF. AEs should be followed to resolution or stabilization (if possible), and reported as serious AEs (SAEs) if they become serious.

The investigator will instruct the subject to report any adverse events that may occur during the study. At each visit, the investigator should ask the subject, in non-directive fashion, about any change in the subject's overall condition since the previous visit.

The severity of each AE, as judged by the investigator, will be recorded on the appropriate AE CRF and will be graded according to the following scale:

Mild - The adverse event is transient and easily tolerated by the subject.

Moderate - The adverse event causes the subject discomfort and interrupts the subject's usual activities.

Severe - The adverse event causes considerable interference with the subject's usual activities, and may be incapacitating or life-threatening.

The investigator must determine the relationship of the AE to the test article according to the following categories:

Definite - An event that follows a reasonable temporal sequence from administration of the test article; that follows a known or expected response pattern to the test article; and that is confirmed by improvement on stopping or reducing the dosage, and reappearance of the event on repeated exposure (re-challenge).

Probable - An event that follows a reasonable temporal sequence from administration of the test article; that follows a known or expected response pattern to the test article; and that is confirmed by improvement on stopping or reducing the dosage of the test article; and that is unlikely to have been caused by concurrent/underlying illness or other drugs, procedures, or other causes.

Possible - An event that follows a reasonable temporal sequence from administration of the test article; that follows a known or expected response pattern to the test article; but may have been caused by concurrent/underlying illness, other drug, procedure, or other causes.

Unlikely - An event that does not follow a reasonable temporal sequence from administration of the test article; that does not follow a known or expected response pattern to the test article, or most likely was caused by concurrent/underlying illness, other drug, procedure, or other causes, because of their known effects.

Not Related - An event almost certainly caused by concurrent/underlying illness, other drug, procedure, or other causes.

The investigator should categorize the outcome of the AE according to the following categories:

Fatal - Termination of life as a result of an AE.

Not Recovered/Not Resolved - AE has not improved or the subject has not recuperated.

Recovered/Resolved - AE has improved or the subject has recuperated.

Recovered/Resolved with Sequelae - subject recuperated but retained the pathological conditions resulting from the prior disease or injury.

Recovering/Resolving - AE is improving or the subject is recuperating.

Unknown - Not known, not observed, not recorded or subject refused.

An **adverse reaction** is any AE caused by a drug. Adverse reactions are a subset of all suspected adverse reactions for which there is reason to conclude that the drug caused the event. For the purposes of prescription drug labeling, the term adverse reaction means an undesirable effect, reasonably associated with the use of a drug that may occur as part of its pharmacological action or may be unpredictable in its occurrence.

A **suspected adverse reaction** is any adverse event for which there is a reasonable possibility that the drug caused the event.

For the purposes of IND safety reporting, "reasonable possibility" means there is evidence to suggest a causal relationship between the drug and the adverse event. A suspected adverse reaction implies a lesser degree of certainty about causality than adverse reaction, which means any adverse event caused by a drug.

An adverse event or suspected adverse reaction is considered "unexpected" if it is not listed in the investigator brochure or is not listed at the specificity or severity that has been observed; or, if an investigator brochure is not required or available, is not consistent with the risk information described in the general investigational plan or elsewhere in the current application. For example, under this definition, hepatic necrosis would be unexpected (by virtue of greater severity) if the investigator brochure referred only to elevated hepatic enzymes or hepatitis. Similarly, cerebral thromboembolism and cerebral vasculitis would be unexpected (by virtue of greater specificity) if the investigator brochure listed only cerebral vascular accidents. "Unexpected," as used in this definition, also refers to adverse events or suspected adverse reactions that are mentioned in the investigator brochure as occurring with a class of drugs or as anticipated from the pharmacological properties of the drug, but are not specifically mentioned as occurring with the particular drug under investigation.

Adverse skin reactions have been reported with the use of topical corticosteroids and may occur more frequently with high potency corticosteroids such as halobetasol cream and ointment. These reactions include stinging, burning, itching, erythema, acne, dry skin, folliculitis, leukoderma, telangiectasia, pustulation, hypertrichosis, acneiform eruptions,

hypopigmentation, perioral dermatitis, allergic contact dermatitis, vesicles, rash, paresthesia, urticaria, secondary infection, skin atrophy, striae and miliaria. (4, 5, 6).

Systemic absorption of topical corticosteroids has produced reversible HPA axis suppression, manifestations of Cushing's syndrome, hyperglycemia and glucosuria in some patients. In rare instances, treatment (or withdrawal of treatment) of psoriasis with corticosteroids is thought to have provoked the pustular form of the disease (6).

Risks associated with venipuncture and the CST are listed in [Section 13.1](#).

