If only limited information is initially available, follow-up reports are required. Should the investigator become aware of a SAE (regardless of its relationship to test article) that occurs within 30 days after stopping the test article, the SAE must be reported in accordance with procedures specified in this protocol. In the event of death, if an autopsy is performed, a copy of the report should be sent to TI, if available.

As required, TI will notify participating investigators of all suspected adverse reactions that are serious and unexpected. This notification will be in the form of an IND safety report of potential serious risks as soon as possible but no later than 15 calendar days after the Sponsor determines that the information is "reportable" according to the criteria listed in 21 CFR Section 312.32. These are:

- i) Serious and unexpected suspected adverse reactions,
- ii) Findings from other studies including epidemiological studies, pooled analyses or other clinical studies that suggest a significant risk in humans exposed to the test articles,
- iii) Findings from animal or in vitro tests that suggest a significant risk to humans exposed to the test articles, or reports of significant organ toxicity at or near the expected human exposure, and
- iv) Clinically important increases in the rate of occurrence of serious suspected adverse reactions.

Upon receiving such notices, the investigator must review and retain the notice with the Investigator Brochure and immediately submit a copy of this information to the responsible IRB according to local regulations. The investigator and IRB will determine if the informed consent requires revision. The investigator should also comply with the IRB procedures for reporting any other safety information. Where required, submission of safety updates by the investigator to Health Authorities should be handled according to local regulations.

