### **8.9.2 *Adverse Events***

All AEs reported during the study will be listed, documenting onset, whether therapy was required, any change in test article dosing, severity, possible relationship to test article, and outcome. Verbatim terms on the CRFs will be linked to preferred terms (PTs) and system organ class (SOC) using the Medical Dictionary for Regulatory Activities (MedDRA) version 20.0. For all AE summaries, if a subject has more than one AE within a PT, the subject is counted once in that PT. If a subject has more than one AE within a SOC, the subject is similarly counted once in that SOC.

The number and percentage of unique subjects reporting any local and systemic treatment-emergent AE will be summarized by SOC and PT. The number and percent of unique subjects reporting any local and systemic TEAE will also be summarized by SOC, PT, and maximum severity (mild, moderate, severe) and closest relationship to test article (not related, unlikely, possibly, probably, definitely related). AE summaries will utilize the Safety population.

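### All three related causality grades require a recognised response pattern, so a truly new non-serious reaction cannot be graded treatment-related

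*Protocol*

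**What the plan says.** Protocol 15.1 requires the investigator to determine relationship using five categories. The three upper ones share one condition:

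- Definite: a reasonable time sequence and "a known or expected response pattern to the test article; and that is confirmed by improvement on stopping or reducing the dosage, and reappearance" on re-exposure.
- Probable: a reasonable time sequence, other causes unlikely, and "a known or expected response pattern to the test article; and that is confirmed by improvement on stopping or reducing the dosage of the test" […].
- Possible: a reasonable time sequence and an event "that follows a known or expected response pattern to the test article; but may have been caused by concurrent/underlying illness, other drug" or another cause.

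Unlikely covers an event without a reasonable time sequence, one "that does not follow a known or expected response pattern to the test article, or most likely was caused by concurrent/underlying illness" or another cause. Not Related needs an almost certain other cause.

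Protocol 15 fixes which grades count as related: "treatment-related (i.e., definitely, probably, or possibly related to test article".

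Elsewhere in 15.1 a suspected adverse reaction is "any adverse event for which there is a reasonable possibility that the drug caused the event", with no reference to pattern. The definition of an adverse reaction there also allows for effects that could not be predicted. Protocol 15.2 makes "Serious and unexpected suspected adverse reactions" reportable and asks that SAE notifications carry their own judgement on whether the drug may have caused the event.

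SAP 7.3 names the five grades without redefining them. SAP 8.9.2 tabulates treatment-emergent events by SOC, PT and "closest relationship to test article (not related, unlikely, possibly, probably, definitely related".

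**The concern.** Whether a drug caused an event and whether the event was foreseeable are separate questions, and the definitions in 15.1 treat them so. The grading scale does not: it makes a recognised pattern a precondition for any related grade. The reactions affected are those not already known for the product. Protocol 15 gives a fuller understanding of the test article's safety profile as one reason for collecting adverse events, and the lotion study cited in the Background was in adults. In the SAP relationship table, a new reaction in this age group would appear as unlikely, or lack a valid grade, because of the definition and not because of the investigator's view of cause.

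**Working it through.** No arithmetic applies, and the plan has no figure to reproduce. The check takes the definitions in Protocol 15.1 as stated and applies them to a test event.

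Notation: T = reasonable time sequence; P = known or expected response pattern; D = improvement on stopping or reducing; R = recurrence on re-exposure; A = another cause.

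| Grade | Conditions in 15.1 | Related under Protocol 15? |
|---|---|---|
| Definite | T and P and D and R | yes |
| Probable | T and P and D and A unlikely | yes |
| Possible | T and P and A may be the cause | yes |
| Unlikely | (not T; not P) or A most likely | no |
| Not Related | A almost certain | no |

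Test event: a new, non-serious reaction with T true, P false and no other cause.

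1. Definite, Probable and Possible all fail on P. D and R make no difference: even an event that clears on stopping and returns on re-exposure fails Definite.
2. Not Related fails because there is no other cause.
3. Unlikely is met if its first two clauses are alternatives (not T or not P). If they are cumulative (not T and not P), it fails because T is true, and the event has no category.

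On either reading, 0 of the 3 related grades are available.

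The same event set against the other definitions:

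- Under the definition of a suspected adverse reaction in 15.1, it qualifies if there is a reasonable possibility of causation. Plausible timing with no competing cause supports that, and P is not asked for.
- Under 15.2, the extra causality judgement applies only to serious events. For a non-serious event the five-step grade is the only causality record.
- Under SAP 8.9.2, the grade goes straight into the relationship table. Nothing in SAP 7.3 or 8.9.2 changes the definitions.

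One further check bears on the remedy. Possible, read literally, also expects that another cause may be responsible. If only the pattern clauses were removed from Possible and Unlikely, the test event would still miss Possible for want of a competing cause, would still fail Definite and Probable on P, and would no longer fit Unlikely. That clause must change too.

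**The case against.** The strongest reply is that the descriptors guide clinical judgement and were not written as a truth table. Read strictly, they leave other ordinary events without a grade, such as a well-known reaction with no information on stopping and no competing cause. Protocol 15 itself speaks of what the investigator considers related. This has some force, but 15.1 says the grade must be assigned by these categories. Relying on judgement means that sites (about four are planned) may depart from the definitions in different ways.

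The rest of the reply limits the scope, and it stands. Four stronger conclusions that a reader might draw are not supported:

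- *That unexpected serious reactions cannot be identified.* Protocol 15.2 asks for a separate causality judgement on each SAE and ties reportability to a sponsor determination; neither depends on the grade. What remains is that grade and judgement could contradict each other on one record.
- *That no unexpected event can be graded related.* Unexpected in 15.1 is wider than lacking a recognised pattern. It includes class effects not listed for this drug and listed events at greater severity or specificity, and these may still be graded related.
- *That new reactions are followed less closely.* Protocol 15.1 asks that all AEs be followed until they resolve or stabilise, where possible, whatever the grade. The emphasis on treatment-related events in Protocol 15 concerns reporting the outcome of events that led to permanent discontinuation or were present at study end.
- *That related counts are forced to zero, or events lost.* Recognised reactions can still be graded related. Every AE is listed and treatment-emergent events are tabulated by SOC and PT regardless of grade. An abnormal end-of-study cosyntropin test is attributed to the test article by rule (Protocol 13.1, SAP 7.1), and local skin reactions are summarised by severity without a causality grade.

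**Conclusion.** The scale is wrong as written, with minor consequences. A truly new non-serious reaction cannot reach any of the three related grades, which is inconsistent with the definitions of suspected and adverse reaction in the same section. The error carries into the relationship split in SAP 8.9.2.

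Its size in events cannot be stated. The documents give no rate of reactions without a recognised pattern, and the number may be zero. The damage is limited to misclassification in one descriptive summary, plus a possible contradiction between grade and causality judgement for a new serious event.

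The conclusion assumes that investigators apply the categories as worded and that truly new means outside both the known profile of the lotion and what its pharmacology would lead one to expect. The protocol does not define a response pattern, so a generous reading reduces the number of events affected but does not remove the gap.

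**What to change.** In Protocol 15.1:

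- Redefine Possible as an event with a reasonable temporal sequence, whether or not it fits a recognised response pattern and whether or not another cause may have contributed, that does not meet Probable or Definite and has no clearly more likely other cause.
- Remove the absence of a recognised pattern as a sufficient ground for Unlikely, leaving implausible timing or a more likely other cause.

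Under this wording the test event is Possible, and so is the known reaction with no information on stopping and no competing cause. A new reaction that clears on stopping or recurs on re-exposure would still be graded only Possible, but it would count as related.

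The cost is the wording of two definitions and a note to sites. CRF categories and SAP table layouts do not change. The downside is that the treatment-related AE count may be slightly higher.
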